## 5 For analysis, the EFAS will be used in the same way as the FAS. Protocol Violations

In this registry, the analysis is limited to patients with signed patient informed consent and complete date of patient informed consent (otherwise no further entry in the eCRF was possible) who are scheduled for Phased RFA for AF catheter ablation treatment. Furthermore, the patients have to fulfil the eligibility criteria of an age  $\geq 18$  years as well as a signed PIC/PDRF which allows the analysis of collected personal data during the participation in the registry (up to 14 months after the initial Phased RFA procedure). CRF forms documented 14 months after procedure (440 days) will be ignored for analysis.

In this registry it is not distinguished between a broader full analysis set and a more compliant per-protocol set that excludes all major violators. Therefore, the definition of major violators is not applicable.

# 6 Target Variables

## 6.1 Study Population

Data from all patients who are enrolled in the study (patients who meet the eligibility criteria and signed the PIC/PDRF) will be included in the analysis. If a patient exits from the study, data collected prior to the study withdrawal can be included in the analysis in compliance with PIC/PDRF unless patient requests deletion of the personal data when exit the study in compliance with local regulations.

The following parameters will be used to characterise the study population and to give an overview on the documented visits:

- Overview about patient status
  - number of patients in the All-Documented Patients Set (APS),
  - number of patients in Baseline Analysis Set (BAS),
  - number of patients in Full Analysis Set (FAS)
  - number of patients in Extended Full Analysis Set (EFAS)
- Overview about reasons for being excluded from the different analysis sets
  - Criteria for the BAS
  - Criteria for the FAS
- Number of documented patients per site (BAS)
- Number of documented patients per visit and visit period (FAS)
- Number of documented visits per patient (FAS)
- Number of documented patients by visit pattern (FAS)

A patient is defined as "documented" at a respective visit, if the FU form has a date of the visit and it is non-empty (at least one further entry) for that visit.

## 6.2 Analysis Variables

All appropriate information of the following eCRF sections will be used to characterise the study populations (see Appendix D: Annotated Case Report Form V1.3 and V1.4). Data will be displayed based on their entity type (SAP chapter 7.2).

- Demographics and other Baseline Characteristics, Procedure Documentation
- Follow-up Documentation: General FU
- Follow-up Documentation: 12 Months FU
- Follow-up Documentation: 12MFUby Phone
- Adverse Event Form (SUE form)
- Study Exit Form
- Quality of Life Questionnaires

## 6.3 Quality of Life Questionnaires

In this registry, QoL will be assessed with the *Atrial Fibrillation Effect on Quality of Life* (AFEQT) questionnaire. It is a standardized, disease-specific, reliable and responsive measure of health-related QoL in patients with atrial fibrillation. The AFEQT is a self-reported

questionnaire with responses on a 7-point Likert scale. The 20-item instrument is divided into three domains (a 4-item Symptom score, an 8-item Daily Activities score, a 6-item Treatment Concerns score) plus two Treatment Satisfaction questions. The domains Symptoms, Daily Activities and Treatment can be aggregated into an overall score.

For all questionnaires, the frequencies of the given answers are presented by country and overall. If - based on the answers – scores are constructed these are presented, too.

The AFEQT questionnaire consists of 3 functional subscales (Symptoms [4 items], Daily Activities [8 items], Treatment Concern [6 items]) that are part of the overall AFEQT score. The 2 questions on Treatment Satisfaction are computed as its own subscale similarly to the overall score.

- Symptoms [*not at all bother OR I did not have this symptom; hardly bothered; a little bothered; moderately bothered; quite a bit bothered; very bothered; extremely bothered*]:
  - Palpitations: Heart fluttering, skipping or racing
  - Irregular heartbeats
  - Pause in heart activity
  - Light-headedness or dizziness
- Daily Activities:
  - Ability to have recreational pastimes, sports, and hobbies  
[*not at all limited; hardly limited; a little limited; moderately limited; quite a bit limited; very limited; extremely limited*]
  - Ability to have a relationship and do things with friends and family  
[*not at all limited; hardly limited; a little limited; moderately limited; quite a bit limited; very limited; extremely limited*]
  - Doing any activity because you felt tired, fatigued, or low on energy  
[*no difficulty at all; hardly any difficulty; a little difficulty; moderately difficulty; quite a bit of difficulty; a lot of difficulty; extreme difficulty*]
  - Doing physical activity because of shortness of breath  
[*no difficulty at all; hardly any difficulty; a little difficulty; moderately difficulty; quite a bit of difficulty; a lot of difficulty; extreme difficulty*]
  - Exercising  
[*no difficulty at all; hardly any difficulty; a little difficulty; moderately difficulty; quite a bit of difficulty; a lot of difficulty; extreme difficulty*]
  - Walking briskly  
[*no difficulty at all; hardly any difficulty; a little difficulty; moderately difficulty; quite a bit of difficulty; a lot of difficulty; extreme difficulty*]
  - Walking briskly uphill or carrying groceries or other items, up a flight of stairs without stopping  
[*no difficulty at all; hardly any difficulty; a little difficulty; moderately difficulty; quite a bit of difficulty; a lot of difficulty; extreme difficulty*]
  - Doing vigorous activities such as lifting or moving heavy furniture, running, or participating in strenuous sports like tennis or racquetball  
[*no difficulty at all; hardly any difficulty; a little difficulty; moderately difficulty; quite a bit of difficulty; a lot of difficulty; extreme difficulty*]
- Treatment Concern [*not at all bother; hardly bothered; a little bothered; moderately bothered; quite a bit bothered; very bothered; extremely bothered*]:

- Feeling worried or anxious that your atrial fibrillation can start anytime
- Feeling worried that atrial fibrillation may worsen other medical conditions in the long run
- Worrying about the treatment side effects from medication
- Worrying about complications or side effects from procedures like catheter ablation, surgery, or pacemaker therapy
- Worrying about side effects of blood thinners such as nosebleeds, bleeding gums when brushing teeth, heavy bleeding from cuts, or bruising
- Worrying or feeling anxious that your treatment interferes with your daily activities
- Treatment Satisfaction [*extremely satisfied; very satisfied; somewhat satisfied; mixed with satisfied and dissatisfied; somewhat dissatisfied; very dissatisfied; extremely dissatisfied*]:
  - How well your current treatment controls your atrial fibrillation
  - The extent to which treatment has relieved your symptoms of atrial fibrillation

For the scoring of the AFEQT, see chapter 7.4.3 in the SAP.

### 6.3.1 Ensure AFEQT data quality for analysis

The following test procedure is planned to admit the use of the AFEQT questionnaire in the GOLD AF registry. Prior analysis, possible effects are needed to discover regarding the following issues:

- a. the use of AFEQT data from not validated language versions
- b. the use of AFEQT data that were not self-administered by the patients, but documented by sites in telephone interviews.

#### Step 1: Validated and not validated AFEQT language versions

The following language versions used in this registry are validated: French, German, Italian, Spanish, Polish, Dutch, English and Korean. The following language versions used in this registry are not validated: Georgian, Greek, Hungarian, Hebrew, Arabic, Russian and Portuguese.

To evaluate whether validated and not validated language versions differ from each other, baseline AFEQT scores will be compared between both groups, i.e. evaluation of homogeneity of both distributions (Wilcoxon-Mann-Whitney test, two tailed,  $p<0.05$ ). It will be assumed, that both patient sets are equal in their medical history. Further predictors or confounders will not be considered. If the difference proves to be statistically significant, data derived from not validated language versions will be excluded from further analyses. Otherwise, step 2 will be evaluated.

#### Step 2: Self-administered and interview data

The AFEQT was developed and validated as a self-administered questionnaire. However, a currently unknown number of AFEQT questionnaires (i.e. especially those documented during hospital visits) will be collected by the sites and at the 12 months follow-up by phone AFEQT questionnaires will be documented during telephone interviews.

To evaluate whether self-administered and interview data differ from each other, data from both groups (self-administered vs. interview) will be compared (i.e. evaluation of homogeneity of distributions, Wilcoxon-Mann-Whitney test, two tailed,  $p<0.05$ ). If the difference proves to be statistically significant, data from both groups will not be merged, but analysed separately.

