- Treated with the PVAC GOLD catheter only in persistent AF patients

Evaluate QoL (AFEQT) dynamic through 12 months.

Rational: Symptom relief and improvement in QoL are the major therapeutic goals of PVI. The validated AFEQT questionnaire designed specifically to assess the impact of AF burden on patient's QoL. Improvement in QoL will be used as a subjective indicator of Phased RFA long term success.

Endpoint definition: AFEQT questionnaire completed at baseline and at 12 months FU.

Analysis Methods: Change in QoL from baseline to 12 months will be summarized using mean, SD, minimum, median, maximum and IQR. Statistically significant change from baseline will be assessed using a two-sided t-test.

Limitations: If QoL was completed at baseline, but missed for 12 months FU, this patient will be excluded from the analysis. As far as QoL is not a standard of care in some hospitals it is up to patient consideration to complete or to refuse QoL completing.

5 Project Termination

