**Structure and consequences of planned tests:**

Scenario 1: Statistically significant difference between validated and not validated language versions

→ Exclusion of data from not validated language version from all further analyses

Scenario 2: No statistically significant difference between validated and not validated language versions

→ Merging and release AFEQT data for step 2

Scenario 3: Statistically significant difference between self-administered and interview data, but no statistically significant difference between validated and not validated language versions

→ Merging of AFEQT data from validated and not validated language versions and separate analyses of data from both groups (self-administered vs. interview) regarding all further analyses

Scenario 4: No statistically significant difference between self-administered and interview data and no statistically significant difference between validated and not validated language versions

→ Merging of AFEQT data from validated and not validated language versions and merging of data from both groups regarding all further analyses

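### The AFEQT mode comparison (SAP 6.3.1 Step 2) fixes neither the visit nor the unit of grouping, so run on all forms it would read change over time as an interview effect

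*SAP*

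**What the plan says.** SAP 6.3.1 sets two checks before AFEQT data are used. Step 1, on language versions, fixes its visit: "baseline AFEQT scores will be compared between both groups". Step 2, on mode of administration, says only this: "To evaluate whether self-administered and interview data differ from each other, data from both groups (self-administered vs. interview) will be compared", with "evaluation of homogeneity of distributions, Wilcoxon-Mann-Whitney test, two tailed" at the 0.05 level. It names no visit, no score and no rule for placing a patient or a form in a group. On timing it says that "at the 12 months follow-up by phone AFEQT questionnaires will be documented during telephone interviews". It also mentions an unknown number of forms collected by sites, mainly at hospital visits, without saying which mode they count as.

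The consequence is: "If the difference proves to be statistically significant, data from both groups will not be merged, but analysed separately". Scenario 3 repeats this as "separate analyses of data from both groups (self-administered vs. interview) regarding all further analyses".

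Three other places bear on this:
- Protocol 7.2 (Baseline) has the patient complete the baseline AFEQT.
- SAP Table 2 and SAP 8.3.5 define the quality-of-life result as the difference between baseline and 12 months, and Table 2 allows the phone follow-up as the later value.
- Protocol 3.5 requires every AFEQT analysis both overall and stratified by mode, with no test beforehand.

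**The concern.** Telephone forms are essentially post-ablation forms, while the self-administered forms include the baselines. A comparison with no visit restriction therefore mixes the effect of mode with change since ablation. Protocol 4.4.3 treats improvement in quality of life as a goal of treatment and an indicator of success, so some change is the expected case.

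Two things are at stake. First, the merge-or-split decision for every later AFEQT analysis could be wrong in either direction: a split with no mode effect, or a merge when improvement hides a real one. Second, if the split is made form by form, a phone patient's baseline lands in one set and the 12-month score in the other, and the required change score cannot be formed inside either set.

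**Working it through.** The documents give no AFEQT standard deviation, expected change, phone share or power for this check, so there is no planned figure to reproduce. The inputs below are assumptions, apart from the two-tailed 0.05 rule (SAP Step 2) and N = 800. That N is the planned evaluable number in Protocol 4.3; it was derived for re-ablation and is not a count of AFEQT completers.

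**Which visit could Step 2 mean?**
- Baseline only, as in Step 1: it would hold little or no telephone data and could not answer the question.
- 12 months only: it compares different patients at the same visit and works.
- All forms, as the sentence literally reads: visit and mode are mixed.

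**Size of the artefact if all forms are compared.** Let f be the phone share at 12 months, d the true change in SD units and rho the within-patient correlation. Take all baselines as self-administered and no true mode effect.
- The interview mean is d. The self-administered mean is d(1−f)/(2−f). The spurious difference is d/(2−f), which is 53%, 56%, 67% and 100% of the true change at f = 10%, 20%, 50% and 100%.
- The true variance of that difference is [1/f + 1/(2−f) − 2·rho/(2−f)²]/N. An unpaired test assumes [1/f + 1/(2−f)]/N.
- For f = 0.5, rho = 0.5, N = 800: true SE = √(2.222/800) = 0.0527; assumed SE = √(2.667/800) = 0.0577; rejection threshold = 1.96 × 0.0577 = 0.113.
- At d = 0.2 the spurious difference is 0.133, and (0.133 − 0.113)/0.0527 = 0.38, so rejection is about 65%. At d = 0.3 it is 0.200, and (0.200 − 0.113)/0.0527 = 1.65, so about 95%.

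Simulating the rank test itself (1,000 runs per cell, N = 800, rho = 0.5) gives slightly lower rates, in line with this approximation based on means:

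| Phone share | 0.1 SD | 0.2 SD | 0.3 SD | 0.5 SD |
|---|---|---|---|---|
| 30% | 12% | 35% | 73% | 99% |
| 50% | 16% | 61% | 94% | 100% |
| 80% | 33% | 94% | 100% | 100% |

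At N = 400 and 50% phone the rates are 11%, 35%, 67% and 98%. A separate simulation on the 0–100 scale (assumed SD 20, N = 800) gives 37% at a 5-point change and 90% at 10 points with 20% phone, and 18% and 59% with 10% phone.

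**Same test on 12-month scores only.** Rejection is 4.5–5.4% across N = 300 or 800, phone share 20% or 50%, and change 0 or 20 points.

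**Masking.** Take d = 0.5 SD, a true phone effect of −0.3 SD and f = 0.5. The interview mean is 0.2 and the self-administered mean is 0.5 × 0.5/1.5 = 0.167, leaving a difference of 0.033 SD. The test on all forms detects this 7% of the time, against 98.5% on 12-month scores.

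**Is the unpaired test the cause?** No. With no change and 50% phone, the test on all forms rejects about 4.4%, 4.1%, 3.4% and 2.4% at rho = 0, 0.3, 0.5 and 0.7. Ignoring the pairing makes it slightly conservative. With rho = 0 and 20% phone it still rejects 38% at 5 points and 89% at 10. The missing visit restriction drives the result.

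**Scenario 3 applied to forms.** The interview set holds no baselines, hence no change scores. The self-administered set keeps 800(1−f) pairs: 720, 640 or 400 at 10%, 20% or 50% phone.

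**The case against.** The strongest reply is that the SAP never orders visits to be pooled. It speaks of two groups, uses a test for independent samples and names the 12-month phone follow-up as the interview setting; Step 1 uses the same language for groups of patients. A comparison between patients at 12 months fits that wording and holds its 5% level. This stands: the defect is an unspecified rule, and the error rates above belong to one reading of it.

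A reader might also infer that phone patients necessarily drop out of the change analysis. The documents do not support that. If patients are grouped by 12-month mode, each keeps the baseline score, and Table 2 and SAP 8.3.5 presuppose such pairs. The exclusion in Protocol 4.4.3, "If QoL was completed at baseline, but missed for 12 months FU, this patient will be excluded from the analysis", concerns missing 12-month questionnaires, not telephone ones.

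Nor is it certain that interviews occur only at 12 months. Protocol 3.5 mentions telephone administration at some sites without naming a visit, and the site-collected hospital forms have no stated mode. If some baselines counted as interview data, mode and visit would be less closely tied and the artefact would change in size.

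Finally, this is a preliminary check for one ancillary objective in a descriptive registry. That limits its weight. But Step 2 decides how every later AFEQT analysis is built, and nothing in its text directs the programmer to the reading that works.

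**Conclusion.** The point holds as a gap in specification with a material consequence. Step 2 leaves open the visit and the unit of grouping. Applied to all forms, it attributes 53–100% of any change over time to mode, depending on phone share (10–100%). With 800 patients, 50% phone, correlation 0.5 and no true mode effect, it then rejects about 61% of the time at 0.2 SD and 94% at 0.3 SD; restricted to 12-month scores it rejects about 5%. These rates rest on assumed inputs and on all baselines being self-administered.

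It would be too strong to say that the SAP prescribes pooling, that the unpaired test is the fault, or that change scores are lost on every reading. What does not depend on the reading is that the SAP makes separation by mode conditional on a significance test, while Protocol 3.5 requires overall and mode-stratified results regardless. The main objective and safety are untouched.

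**What to change.** In SAP 6.3.1:
1. Restrict Step 2 to 12-month AFEQT scores, and classify each patient once, by the mode used at 12 months.
2. Compare modes with adjustment for the patient's own baseline score (analysis of covariance). A site effect is optional, because mode may be largely confounded with site.
3. In Scenario 3, analyse patients grouped by 12-month mode, each keeping the baseline score whatever its mode, so that change is computed in both groups.
4. State which mode group the site-collected hospital-visit forms join.
5. Reconcile the significance rule with Protocol 3.5: either report overall and mode-stratified results in all cases, or record and justify the departure.

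The cost is SAP wording and one regression on data already collected. Patients without a baseline AFEQT do not enter the adjusted comparison. Mode remains non-randomised, so even the corrected comparison describes a difference between patient groups and does not isolate the effect of interviewing.

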**Structure and consequences of planned tests:**

Scenario 1: Statistically significant difference between validated and not validated language versions

→ Exclusion of data from not validated language version from all further analyses

Scenario 2: No statistically significant difference between validated and not validated language versions

→ Merging and release AFEQT data for step 2

Scenario 3: Statistically significant difference between self-administered and interview data, but no statistically significant difference between validated and not validated language versions

→ Merging of AFEQT data from validated and not validated language versions and separate analyses of data from both groups (self-administered vs. interview) regarding all further analyses

Scenario 4: No statistically significant difference between self-administered and interview data and no statistically significant difference between validated and not validated language versions

→ Merging of AFEQT data from validated and not validated language versions and merging of data from both groups regarding all further analyses

## 7 Data Handling

This chapter contains instructions for data handling which are generally decisive for derived variable calculations and data presentation.

The basis for time calculations will be the first documented procedure (SAP chapter 7.4.1).

In order to assess the effects of patients lost to follow-up, percentages of dropouts and reason for loss to follow-up will be summarized. In addition, baseline characteristics of patients who were lost to follow-up in comparison to patients with a complete follow-up will be described (SAP chapter 8.6). Patients who withdrawal the PIC/PDRF will be handled according to SAP chapter 6.1.

### 7.1 Definitions

#### Pre-post differences

Pre-post differences in absolute values (also called absolute changes) will always be calculated as post-baseline value minus baseline value.

#### Relative pre-post differences

Relative pre-post differences (also called percent changes) will always be calculated as  $100\% \text{ (post-baseline value minus baseline value) / baseline value}$ .

Pre-post differences will be calculated for the following variables (other can be proposed retrospectively):

**Table 2:** Variables for pre-post differences

Variables	Pre- value	Post- value	Derived variables
Antiarrhythmic medication Anticoagulation medication Antiplatelets Other cardiovascular medication	Discharge	12MFU visit/ 12MFU by phone	Number of patients 
 
• Never on
 
• Newly on
 
• Continued
 
• Discontinued
 

AFEQT-Score	Baseline	12MFU/ 12MFU by phone	Absolute change in AFEQT score
AF burden	Baseline	12MFU visit/ 12MFU by phone	Absolute change in AF burden [%]
EHRA AF symptoms classification	Baseline	12MFU visit/ 12MFU by phone	

## 7.2 Handling data entity types

The CDISC data export is arranged according to the tables in the eCRF (see Data Management Plan). These tables contain data of entities, whose definitions only partially correspond to the entity types processed in statistical analysis. The aim of the analysis is to show the data at patient level.

The following entity types can be used for statistical analysis:

1. Patient
2. Procedure
3. Follow-up
4. Adverse Event

### 7.2.1 Patient data

Data will be analysed showing data on patients level according the eCRF segments enrolment, demographics, medical history, concomitant diseases, diagnostics, medication, hospital discharge, quality of life (AFEQT) and study exit.

